Hypothesis 2A: Changes in hip and knee kinematics and kinetics (frontal and transverse plane hip moment, frontal plane knee motion, and sagittal plane knee motion) will vary by treatment group, with the greatest changes occurring in the Targeted neuromuscular training (TNMT) > Standard of care (STAN) > HOME groups. Hypothesis 2B: Changes in clinical performance measures (hop symmetry; quadriceps and hip abductor

and extensor strength; single limb balance and self-reported function) will vary by treatment group, with the greatest changes in the TNMT > STAN > HOME groups.

Exploratory Aim. Develop a clinical algorithm that classifies patient risk for second ACL injury.

Hypothesis EA: Clinical tests of strength (quadriceps and hamstrings), balance, 2D jump landing mechanics (frontal and sagittal plane knee angle), and knee laxity) will effectively identify patient risk for second ACL injury.

Background

Importance of the problem. Second ACL injury, whether it is an insult to the ipsilateral graft or the contralateral ligament, is a growing problem after reconstruction. Besides missing an additional year of athletic participation, increasing health care costs, and increased psychological distress, re-injury and subsequent revision surgery have significantly worse outcomes compared with those after initial reconstruction.⁸⁻¹⁰ Second injuries have been reported to occur at a rate of 1 in 17 (6%) within the first two years of surgery.²⁶ However, a second tear prevalence of 29% has been reported.^{5-7, 27} This is substantially higher than initial ACL injuries, reported to occur at a rate of 1 in 60 to 100.^{28, 29} Risk factors for second injury include younger athletes⁶ who return to high-level sporting activities early.^{27, 30} Both sexes are at risk for second ACL injury, with females reported as having higher risk of contralateral injury,^{15, 26} and males having an increased risk of ipsilateral injury.^{8, 31, 32} Thus, it is critical to include both sexes in second ACL injury prevention programs.

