B. Strength will be measured on both limbs using a clinical dynamometer (either Humac, CSMi, Stoughton, MA, or Biodex System, Biodex, Shirley, NY).

1. Isokinetic quadriceps and hamstrings strength: Subjects will be seated on the dynamometer with the hip and knee flexed to 90°. Prior to testing, they will undergo a short warm-up. A test session will consist of 10 repetitions at slow (180°/sec) and fast (300°/sec) speeds through a knee range of motion of 0-100°. Peak flexion and extension torques will be recorded.

2. Isokinetic hip abduction strength: Subjects will stand in front of the rotating arm of the dynamometer. A test session will consist of two test sets of 5 repetitions at 120°/second moving into abduction. Peak abduction torque will be recorded.

3. Isometric hip abduction strength: Isometric abduction strength will be collected using a custom force sensing strap. Subjects will stand with their feet placed shoulder-width apart, their knees aligned directly above each foot, and hips and knees slightly flexed. A non-stretchable athletic wrap will be secured around the subject's thighs, superior to the femoral condyles and patella, and secured with tape or Velcro. Three practice repetitions will be conducted in which the subjects will maximally abduct their thighs and push out against the wrap.⁵ maximum efforts will be conducted and recorded. A strain gauge will measure induced voltage and display force output on a monitor. Maximum abduction force in all 5 trials will be recorded.

C. Patient functional performance will be evaluated with a battery of hop tests. Reliability of the unilateral hop tests is good, with ICC coefficients ranging from .^{92-96,85,86}

1. Single leg hop for distance tests: The limb symmetry indexes (LSIs) for the single hop, cross-over hop, and triple hop tests are all based on the maximum distance jumped with a controlled landing, and performance will be calculated by dividing the distance hopped on the involved leg by the distance hopped on the uninvolved leg. Hop distance will be measured to the nearest centimeter on a standard measuring tape secured to the floor. The maximum hop distance of two trials will be used for analysis.

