2. Single leg timed hop: The 6-meter timed hop is a measure of how fast it takes the athlete to hop 6-meters on one leg. A handheld or digital timing system will be used by a trained tester. The 6-meter timed hop LSI will be calculated by dividing the time recorded for the uninvolved (or dominant leg) divided by the time recorded for the involved leg.

D. Skeletal maturity will be evaluated with a modified Pubertal Maturation Observational Scale (PMOS). Maturational categories will include prepubertal (equivalent to Tanner^{87, 88} Stage 1), early pubertal (equivalent to Tanner Stages 2 and 3) or late or postpubertal (equivalent to Tanner Stages 4 and 5). The categories are

based on several indicators of pubertal maturation (growth spurt, menarchal status, body hair, sweating, and muscular definition).⁸⁹ The scale reliably classifies subjects into developmental stages and is based on parental/participant report, and investigator observations.⁹⁰ The reliability of the scale has been demonstrated to be high.⁸⁹

F. Passive anterior knee laxity will be captured with a GNRB arthrometer (Genourob, Laval, France) or a Blue Bay arthrometer (Blue Bay Research Inc, Navarre, FL, USA) using an automated 134 N anterior push on the posterior aspect of the tibia or a Blue Bay arthrometer (Blue Bay Research Inc, Navarre, FL, USA) using a 134 N anterior pull on the tibia.

Tracking

During the six weeks of training, patients will be contacted weekly via email or text message. The surveys will include questions of compliance and involvement of sport activities. If the patient prefers, the surveys can be conducted over the phone rather than on the computer. The coordinator will call the patient/guardian if the survey has not been filled out after two notices. Post training, the patient will receive monthly surveys of injury surveillance for two years. Then yearly follow up for 4 years. Patients will be followed a total of 6 years.

Check all that apply. If none apply, leave blank:

This is a multisite study involving Mayo Clinic and non-Mayo Clinic sites.

When checked, describe the research procedures/activities being conducted **only** at Mayo Clinic:

Mayo Clinic staff will be engaged in research activity at a non-Mayo Clinic site. *When checked, provide the location and a detailed description of the Mayo Clinic research staff involvement.*

This study is to establish and/or maintain an ongoing database or registry for research purposes only.

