Subject population (children, adults, groups): All subjects will be patients who undergo primary ACL reconstruction, and will be recruited from the practices of the sports medicine surgical team at Mayo Clinic, Rochester, MN, as well as the practices of the surgeon affiliates of the sports medicine team at Cincinnati Children's Hospital Medical Center, Cincinnati, OH. Recruitment will also include primary ACL reconstruction patients from the sports medicine surgical team at the University of Minnesota, Minneapolis, MN, and primary ACL reconstruction patients from the sports medicine surgical team at Mayo Clinic Health System, La Crosse, WI. This will include male and female patients between the ages of 13 and 30 years in age

at the time of injury. The University of Minnesota and Mayo Health System locations will serve only as referral sites as no research activity will occur there.

Inclusion Criteria:

1. Age, 13 \geq 30 years, 2. Acute, first-time, isolated ACL injury, 3. No history of previous knee surgery to either extremity, 4. No low back or lower extremity injury in the year prior to ACL injury necessitating medical care, 5. Pre-injury participation in cutting, jumping or pivoting sports for \geq 50 hours/year, 6. Plan to return to full participation in sports following ACL reconstruction.
7. Mechanism of injury did not involve a direct blow to the knee

Patients who sustain a medial collateral ligament (MCL) injury are eligible for study participation if medial knee instability is resolved prior to surgery.

This age range is selected secondary to the majority of ACL injuries occurring in young, active individuals who participate in jumping, cutting and pivoting sports on a regular basis.

Patients with simple meniscus tears (i.e., 2 cm vertical longitudinal tear) that do not necessitate alterations in rehabilitation will be eligible for study participation.

Exclusion Criteria:

Patients with complex, repairable meniscus tears (i.e., radial or root repair), multi-ligament repair, and patients with full thickness articular cartilage lesions will not be eligible for participation.

Research Activity

Check all that apply and complete the appropriate sections as instructed.

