Check 'None' when none of the identifiers listed above will be recorded, maintained, or shared during the conduct of this study. (exempt category 4)	 None	 None

Data Analysis

Power analyses and study endpoints are not required for minimal risk research, pilot or feasibility studies.

No statistical information. *If checked, please explain:*

Power Statement:

We expect that the minimal clinically significant effect size of TNMT on knee biomechanics is 0.17 or above. Using an a priori power analysis based on repeated measures ANOVA, we expect that to achieve 80% power with $\alpha = 0.05$, this study will require a final accrual of 87 subjects. This assumes a correlation coefficient of 0.3 among the repeated measures, which is likely conservative. Thus, an accrual of 116 (with an estimated 30% dropout rate) subjects will be sufficient to determine if a clinically significant reduction in unininvolved limb transverse plane hip net moment impulse, frontal plane knee joint ROM, initial contact sagittal plane knee moment asymmetry, and deficits of involved limb postural stability has occurred as a result of TNMT. This sample size provides adequate power for all variables of interest for Aims 1 and 2. Mayo Clinic averages more than 120 ACLR per year in the Minneapolis/Rochester region on individuals under age 25. Thus, the available patient pool is more than adequate to meet study requirements.

Data Analysis Plan:

Aim 1: We will utilize normal mixture based clustering analysis⁷⁰ to identify groups with distinguished risks based on a priori covariates (i.e., demographics and biomechanical variables). Our previous work used a similar approach to effectively cluster subjects into three distinct risk groups. We intend to confirm disparate risk for injury by assessment of the magnitude of differences across groups using knee and hip abduction angles, surrogates for ACL injury.

The normal mixture model approach works by assuming the density of the covariates for a subject x , can be described as:

$$f(x) = \sum_{k=1}^K \pi_k \phi(x; \mu_k, \Sigma_k),$$

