where (i) K is the number of mixture components (groups), (ii) π_k is the unconditional probability that a subject fall into the k th group, and (iii) $\phi(\cdot; \mu, \Sigma)$ is the multivariate normal density with mean μ and covariance Σ . Estimates of the parameters, π_k, μ_k, Σ_k , are typically obtained using maximum likelihood. The number of groups is most commonly chosen to optimize the Bayesian Information Criterion (BIC). Often assumptions such as a common covariance matrix for all k , or common shape (i.e., correlation) matrix, are made to make estimation feasible, depending on the size of data, and these decisions are also commonly made on the basis of BIC. In this work we intend to assume a common Σ , and assess the validity of this assumption via model diagnostics. Once parameter estimates are obtained, clustering is performed by calculating the probability of group membership m for a given subject, conditional on his/her covariate values, i.e.,

$$P(m = k | x) = \frac{\pi_k \phi(x; \mu_k, \Sigma_k)}{\sum_{l=1}^K \pi_l \phi(x; \mu_l, \Sigma_l)}.$$

The subject will then be assigned to the group k that results in the largest conditional group membership probability $P(m = k | x)$. This approach has been shown to perform very well in the presence of a large number of variables with the inclusion of a variable selection mechanism.^{71, 72} We will leverage such an approach in our analysis to identify a reduced set of biomechanical variables that most informatively differentiate the subjects.

Aim 2:

Aim 2 will utilize a prospective, single blind, randomized clinical trial design. Subjects from Aim 1 will comprise the study sample. Subjects will undergo testing twice.

We will use a repeated-measures ANOVA model with between-subjects factors that include interactions, to determine the effect of TNMT compared to HOME or STAN treatment on clinical performance after ACLR. Specifically, for a response of interest y , e.g., hip abductor strength, for the i^{th} subject in the k^{th} treatment group, with $l = 0$ indicating before intervention and $l = 1$ indicating after,

$$y_{ikl} = \alpha + \delta_l + (\gamma\delta)_{kl} + \tau_{i(k)} + \epsilon_{ikl}$$

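### The Aim 2 model leaves out sex and age, which the trial already collects; adding them would give a small gain in precision and would not correct a bias.

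*Combined protocol and SAP*

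**What the plan says.** The Data Analysis Plan for Aim 2 describes a "repeated-measures ANOVA model with between-subjects factors that include interactions" and writes it out: intercept, time, arm-by-time, a random subject effect and error. The time and arm-by-time terms are set to zero at Pre-Testing, so all arms share one baseline mean. The plan then adds that the same inference could be had from a one-way ANOVA of the pre-post differences. The equation contains no patient characteristic. The sentence on primary inference does name risk group and its interaction with arm, but the printed model has no such term.

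The Subject Information section defines the population as "male and female patients between the ages of 13 and 30 years in age". The Background states: "Both sexes are at risk for second ACL injury, with females reported as having higher risk of contralateral injury". It also calls age a significant factor for second rupture. In the Clinical Testing Protocol, quadriceps and hamstrings strength is taken as torque ("Peak flexion and extension torques will be recorded"), and no scaling to body size is stated. The account of randomisation under Study Design and Methods mentions no stratification. Birth dates are among the recorded identifiers, and Aim 1 already uses demographics as covariates.

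**The concern.** Where a baseline characteristic predicts the outcome and is already on file, putting it in the model usually narrows the treatment contrast without more patients. Raw torque in males and females from early adolescence to adulthood is an outcome for which sex and age could plausibly matter. The plan also assumes a pre-post correlation of only 0.3. At that value the Pre-Testing result removes just 0.3² = 9% of Post-Testing variance, which leaves room for other predictors. What is at stake is the width of the confidence interval for the arm contrast in a trial with few patients per arm.

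**Working it through.** **The plan's own figure.** The Power Statement takes a "minimal clinically significant effect size of TNMT on knee biomechanics is 0.17 or above", a correlation of 0.3, 80% power and alpha 0.05, and arrives at 87 subjects. I read 0.17 as Cohen's f, since the scale is not stated, with three arms and two tests. The noncentrality for the arm-by-time test is f²·N·m/(1 − ρ), with m = 2. This gives a required N of 120, and 65.1% power at 87. A value of 87 appears if the correlation is 0.5. That discrepancy is a separate matter, and the calculation below does not rest on it.

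**Inputs**
- Correlation ρ = 0.3 (Power Statement), with 0.7 as a contrast.
- Completers: 150 × (1 − 0.30) = 105, or 35 per arm if the arms are equal. This is an assumption. The Target accrual text says 120 and the Power Statement 87, and patients living at a distance enter only HOME or STAN.
- R, the share of outcome variance explained by sex and age at each test: 5%, 10% or 20%. This is an assumption; the documents give no value.

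**Common-baseline mixed model, as printed**
- Contrast variance using baseline only is proportional to 1 − ρ².
- With sex and age added, ρ' = (ρ − R)/(1 − R), and the variance is proportional to (1 − R)(1 − ρ'²).

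| ρ | R | ρ' | Without terms | With terms | Reduction |
|---|---|---|---|---|---|
| 0.3 | 5% | 0.263 | 0.910 | 0.884 | 2.8% |
| 0.3 | 10% | 0.222 | 0.910 | 0.856 | 6.0% |
| 0.3 | 20% | 0.125 | 0.910 | 0.788 | 13.5% |
| 0.7 | 5% | 0.684 | 0.510 | 0.505 | 0.9% |
| 0.7 | 10% | 0.667 | 0.510 | 0.500 | 2.0% |
| 0.7 | 20% | 0.625 | 0.510 | 0.488 | 4.4% |

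At ρ = 0.3 the gain is worth 105 × (0.910/0.884 − 1) ≈ 3 completers, and by the same sum about 7 and 16.

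**Cost of estimating the terms.** With 105 completers, a baseline-adjusted comparison of three arms leaves 105 − 4 = 101 residual degrees of freedom, and 99 once sex and age are added. The variance is therefore inflated by about 101/99 = 1.02. The net reductions at ρ = 0.3 are about 1%, 4% and 12%. Simulation agrees within its error (about 0.5%, 5% and 12%). At ρ = 0.7 the same factor gives about a 1% loss, no change, and a 2.5% gain.

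**Change-score ANOVA**
- If sex and age act equally at both tests, the variance of the change is 2(1 − R)(1 − ρ') = 2(1 − ρ), whatever R is. Nothing is gained.
- Simulation with three arms of 35 and a large stable effect (1 SD for sex, 0.5 SD per SD of age) gave a standard error of 0.281 without the terms and 0.285 with them.
- If sex and age instead affect the amount of change (0.5 SD for sex, 0.25 SD per SD of age), the figures were 0.293 and 0.285.
- If they explained 5%, 10% or 20% of the variance of the change, power at 105 would move from 74.1% to 76.4%, 78.7% or 83.5%, on the Cohen's f reading above.

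**The two analyses are not equivalent.** At ρ = 0.3 the change-score variance is 2(1 − 0.3) = 1.40, against 0.91 for the common-baseline model. That is 1.40/0.91 − 1 = 54% more.

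**The case against.** The strongest reply is that the plan names a change-score analysis, in which any lasting difference in level between males and females or between ages, including the effect of body size on torque, drops out. That is correct and it stands. It confines the point to two situations: the mixed model as printed, where at ρ = 0.3 the baseline is only partly subtracted, and any effect of sex or age on the amount of change.

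A reader might infer that chance imbalance in sex or age between small arms distorts the arm effect. The documents do not support that. Under randomisation such imbalance is part of the sampling variance, and the standard error covers it. In the simulations mean bias was about zero and type I error about 5%, with or without the terms. This argument is about chance only; the restricted allocation of distant patients is a different question. Nor is the lack of stratification an error in itself.

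Three further replies also stand in part:
- The plan calls 0.3 probably conservative, and a higher correlation shrinks the gain.
- The Background's remarks on sex and age concern mainly the risk of second injury. They do not show how much of the variance in Aim 2 outcomes the two variables explain.
- Hop symmetry is a ratio of one leg to the other within a person, so little or nothing should be gained there.

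Finally, the text does intend a risk-group term, and risk groups are built partly from demographics. That term is missing from the equation and needs reconciling, but a cluster label would not carry the same information as sex and age.

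**Conclusion.** The point holds as a small improvement. The printed Aim 2 model ignores two baseline variables that the trial already has. Under the common-baseline fit and a correlation of 0.3, using them would cut the variance of the arm contrast by about 3%, 6% or 13% for an assumed 5%, 10% or 20% of variance explained, and by roughly two percentage points less after estimation cost. At a correlation of 0.7 the benefit is 1% to 4% before that cost and close to nil after it, unless sex and age explain a good deal. The result rests on the assumed R, on effects of similar size at both tests, and on 35 completers per arm. It does not call the validity of the Aim 2 comparison into question.

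**What to change.** Before the data are analysed, add sex and age at injury (continuous), each with its interaction with time, as fixed effects in the Aim 2 mixed model with the common baseline. Name that model as the analysis, and remove the statement that the one-way ANOVA of differences is equivalent to it. Keep the model without sex and age as a sensitivity analysis.

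The cost is a line or two of wording and four degrees of freedom (two main effects and two interactions), with no new data. For an outcome unrelated to sex and age, precision falls very slightly: the simulated baseline-adjusted standard error went from 0.231 to 0.233.

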Impact on patient care. One of the factors that contributes to second ACL injury is incomplete or ineffective rehabilitation.⁵⁴ Aberrant neuromuscular and biomechanical patterns are commonly seen up to 2 years after ACLR and may help explain the high rate of second ACL injury.¹¹⁻¹⁶ Deficits in the neuromuscular control of both lower extremities following ACLR have been directly implicated in the risk for second ACL injury¹⁵ and may not only be a result of the initial knee injury and subsequent surgery, but may also characterize the athlete's pre-injury movement patterns. Therefore, identification and subsequent targeted treatment of

aberrant post-ACLR movement patterns for both limbs are critical not only to maximize functional recovery but also to reduce the risk for second ACL injury. Though neuromuscular training programs result in a 73.4% decreased risk of a non-contact primary-ACL injury compared to those who do not participate in neuromuscular training⁵⁵, the efficacy of similar programs for reduction of second-ACL injury risk has not been examined.

An evidence-based targeted neuromuscular training (TNMT) program has been designed to reduce the incidence of second ACL injury. This training program was developed with consideration to modifiable factors related to second-injury risk, the principles of motor learning, and careful selection of the exercises that may most effectively modify aberrant neuromuscular programs. In Aims 2 and 3 of this competing renewal proposal we will evaluate the effects of differential treatment interventions. Notably, we will assess the effectiveness of TNMT, including the utilization of visual and verbal biofeedback. Validation of this evidence-based, late-phase TNMT program may significantly impact clinical practice patterns through its integration in rehabilitation settings, and serve as a critical factor in reduction of second injury risk. Ultimately, determining if less intensive HOME and STAN training programs are effective interventions for patients who are at reduced risk for second ACL injury may prove to be a tremendous time and cost savings for patients and the health-care system.

Study Design and Methods

Methods

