with (i) intercept α , (ii) subject random effect $\tau_{i(jk)} \sim N(0, \sigma_{\alpha}^2)$, (iii) pure error (or noise) $\epsilon_{ijk1} \sim N(0, \sigma_{\epsilon}^2)$, (iv) δ_l is the main effect due to intervention, and (vi) $(\gamma\delta)_{kl}$ is the interaction effect allowing intervention efficacy to vary with intervention type. The fixed effects are constrained such that $\delta_0 = (\gamma\delta)_{k0} = 0$. In this model, the baseline (i.e., pre-treatment) response for an individual is:

$$y_{ikl} = \alpha + \tau_{i(k)} + \epsilon_{ikl}.$$

Thus, the pre- intervention response for a given subject is the same regardless of which intervention group k they were assigned to, since nothing would have happened yet within their intervention group to distinguish them from other groups. Under the formulation in (1), the difference between observations before and after intervention is:

$$d_{ijk} = y_{ijk1} - y_{ijk0} = \delta^* + \gamma_k^* + \epsilon_{ijk}^*$$

where $\delta^* = \delta_1$, $\gamma_k^* = (\gamma\delta)_{k1}$, and $\epsilon_{ijk}^* = (\epsilon_{ijk1} - \epsilon_{ijk0}) \sim N(0, 2\sigma_{\epsilon}^2)$. The primary inference of interest is with respect to the relative efficacy of rehabilitation type γ_k^* and the effect of risk group on intervention efficacy, along with their interaction $(\beta\gamma)_{jk}^*$. Thus, this inference could equivalently be conducted using the pairwise differences in a straightforward one-way ANOVA model. We will assess model assumptions (e.g., normality and constant variance) via residual diagnostics and apply transformations if needed. Where appropriate, we will also utilize Tukey HSD post hoc analysis to further determine significance between groups on intervention effect.

Endpoints

There will be no known direct medical benefits to subjects from participating in this study.

Primary: Completion of all study activities

Secondary: Second injury

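### The Aim 2 inference sentence makes arm, risk group and their interaction jointly primary with no order, while the printed model and Hypotheses 2A/2B cover the arm effect only

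*Combined protocol and SAP*

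**What the plan says.** All references are to the combined protocol and SAP.

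- **Data Analysis Plan, Aim 2, inference sentence.** "The primary inference of interest is with respect to the relative efficacy of rehabilitation type" (`gamma_k*`), followed by "the effect of risk group on intervention efficacy, along with their interaction" (`(beta gamma)_jk*`). Nothing ranks the three effects.
- **Same section, model.** The response model has time, arm-by-time and subject terms. The change-score equation has an overall change, the arm term `gamma_k*` and error. No risk-group or arm-by-risk-group term is defined, although stray `j` subscripts appear and the list of terms skips from (iv) to (vi). The text adds that "this inference could equivalently be conducted using the pairwise differences in a straightforward one-way ANOVA model". Earlier, however, it mentions between-subjects factors with interactions.
- **Same section, multiplicity.** Tukey HSD is offered, where appropriate, as a post hoc comparison between groups. Nothing covers error across different effects.
- **Specific Aims, Hypothesis 2A.** Changes "will vary by treatment group, with the greatest changes occurring in the Targeted neuromuscular training (TNMT) > Standard of care (STAN) > HOME groups". The companion hypothesis, 2B, has the same form. Neither mentions risk group.
- **Power Statement.** The only alpha in the document is here: "to achieve 80% power with $\alpha = 0.05$, this study will require a final accrual of 87 subjects".
- **Background, Impact on patient care.** A longer-term interest is "determining if less intensive HOME and STAN training programs are effective interventions for patients who are at reduced risk for second ACL injury".

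**The concern.** The three effects support different conclusions: that the programmes differ in the change they produce, that risk groups change by different amounts, or that the programmes work differently by risk group. An analyst could fit the one-factor or the two-factor model and cite the same section for either. If the arm effect is null and the interaction is significant, the inference sentence would allow the interaction to be reported as a primary result. That would be a subgroup claim in groups found from the trial's own data, and it bears directly on the Background's interest in less intensive programmes for lower-risk patients. Tukey HSD compares arms with one another and does not control error across three different F-tests.

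**Working it through.** **Inputs.** Three arms (Differential Rehabilitation). Two test sessions (Aim 2 analysis). Alpha 0.05, power 80%, effect size 0.17, correlation 0.3 and 87 completers (Power Statement). Assumptions: 0.17 is Cohen's f, since the metric is not named; there are three risk groups, as in the sponsor's earlier work, since the number is not fixed; and the risk groups are the Aim 1 clusters.

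**1. The plan's own figure.** For an arm-by-time effect, lambda = f² × N × m / (1 − rho) = 0.0289 × 87 × 2 / 0.7 = 7.18. With 2 and 84 df this gives 65% power, and 80% needs 120 completers. The stated 87 comes out at a correlation of 0.5, not 0.3. That discrepancy is a separate matter. Here it matters that the statement sizes the trial for the effect of TNMT and sets no alpha for the Aim 2 tests themselves. With the same lambda, a 4-df interaction would have 52% power. This assumes an equal effect size and has no bearing on false positives.

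**2. The model as printed.** One factor gives one omnibus F-test per outcome. The simulated null rejection rate was 4.7% to 5.1%.

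**3. The analysis as the inference sentence names it.** Three F-tests, each at 0.05, all nulls true:

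- If independent: 1 − 0.95³ = 14.26%. Upper bound: 3 × 0.05 = 15%.
- Simulated with a shared error term (3 × 3 layout on change scores, about 85 to 120 completers, equal and unequal arms and risk groups, 20,000 data sets per setting): 12.9% to 14.4%. Each test alone stayed near 5%.
- For comparison, a Bonferroni split at 0.05/3 = 0.0167 gives 1 − (1 − 0.0167)³ = 4.92%.

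**4. Risk groups built from pre-test data.** Step 3 assigns risk groups independently of change. In this trial Aim 1 uses Pre-Testing data, and several of its variables (frontal-plane knee motion, hip moments, quadriceps strength, single-leg stability) are also Aim 2 outcomes. Change is post minus that same pre-test value. Suppose the clustering score correlates r with the baseline outcome and relates to the post-test only through baseline, with equal variances. Its correlation with change is then −r × √((1 − rho)/2) = −r × √0.35 = −0.59r. That is −0.18 at r = 0.3 and −0.30 at r = 0.5, with no treatment effect at all. The documents do not give r, so both values are illustrative. Simulated with 87 completers, three equal risk groups and rho = 0.3:

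| r | Risk-group test rejects | At least one of three rejects |
|---|---|---|
| 0 | about 5% | about 14% |
| 0.3 | about 23% | about 29% |
| 0.5 | about 58% | about 62% |

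The arm and interaction tests stayed near 5% throughout. The excess is regression to the mean in the risk-group test.

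**The case against.** The strongest objection is that about 14% is not the error rate of the written analysis. The model has one factor, the plan calls it a one-way ANOVA, and the risk-group phrase and `j` subscripts look like remnants of a two-factor version. Deleting the phrase would remove the problem. This stands: the figure is conditional on the two-factor analysis being run. It does not settle the matter, because the sentence that declares the primary inference still names all three effects, and the other obvious repair, adding the missing terms, would create the unordered three-test analysis.

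A reader might also infer that nothing says which effect decides Aim 2, or that a risk-group effect alone would count as success. The documents do not support either reading. Hypotheses 2A and 2B, the stated purpose of the Aim 2 model and the Power Statement all point to the effect of the programmes, and no success rule mentions risk group. Nor does the Background commit the trial to recommending programmes by risk group; its wording is conditional and aspirational.

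Finally, many analysts do not adjust across factorial effects that answer separate questions. That is a fair convention when the effects are labelled as separate questions. Here they are bundled into one primary inference.

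**Conclusion.** The point holds as an inconsistency with a conditional error cost. The inference sentence gives three effects joint primary status without an order, while the printed model and the Aim 2 hypotheses support one. Under the printed model the rate is about 5% per outcome. Under the two-factor analysis it is about 13% to 14% per outcome, assuming each effect is tested at 0.05 (inferred, because alpha appears only in the Power Statement), all nulls are true and risk groups are unrelated to the outcome. If the groups draw on the same pre-test values as the change score, the rate rises, to roughly 29% to 62% at the illustrative correlations of 0.3 to 0.5, entirely through the risk-group test. The tempting stronger claim, that the plan as written runs at nearly three times its stated alpha, does not follow from the documents. Multiplicity across outcomes is a separate matter.

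**What to change.** In the Data Analysis Plan for Aim 2, replace the inference sentence. State that, for each outcome, the only primary inference is the arm effect on pre-to-post change (`gamma_k*`), tested by an omnibus F at alpha 0.05 and followed by Tukey HSD. This matches Hypotheses 2A and 2B. Then do one of the following:

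- delete the phrase on risk group and interaction and tidy the `j` subscripts; or
- add `beta_j` and `(beta gamma)_jk` to the model, drop the one-way ANOVA equivalence, label the interaction secondary or exploratory (estimate with 95% CI), and label the risk-group effect descriptive, noting regression to the mean.

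In either case, state that any recommendation of a programme by risk group is hypothesis-generating.

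The change needs no extra patients, data or procedures, and the arm test keeps its full alpha. The downside is that an interaction seen without an arm effect, including opposing effects across risk groups, cannot be claimed as a confirmed primary result.
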